### 3.9 Relative day

Relative day will be calculated the following way

- for days on or after the day of first dose of study drug and prior to or on the day of last study drug dose:
  - the current date minus the date of first dose of study drug plus 1 (e.g., the day of first dose will be Day 1).
- for days prior to the first dose of study drug:
  - date of first dose of study drug minus the current date (e.g., the day prior to first dose will be Day -1).
- For days after the last dose of study drug:
  - the current date minus the date of last dose of study drug including a “+” to denote posttreatment days (e.g., the day after the last dose will be Day +1).

Relative day will only be computed for fully completed dates and will be missing for partial dates. Two relative days will be used as follows:

- Compared to the first dose of study drug in the Initial Treatment Period for all subjects
- Compared to the first dose of study drug in the Open-Label Extension 2 Period for subjects in OLS2 only.

### 3.10 Changes to protocol-defined analyses

The following endpoints are not listed in the protocol, but have been added to the SAP in order to achieve consistency with other studies from the program:

- Percent of subjects with absolute BSA=0%,  $\leq 1\%$ ,  $\leq 3\%$  and  $\leq 5\%$
- Patient Symptom Diary responses for itch, pain, and scaling

The log-rank statistic for time to PASI response as described in Section 8.3.1.2 will be produced by region and prior biologic exposure although this is not specifically stated in the protocol.

The Treatment Period is further divided into two sub periods -Initial Treatment Period and Maintenance Treatment Period- to aid different analysis summaries and help keep consistency with other studies.

The protocol states that subgroup analyses will be performed on the primary and secondary efficacy variables that are part of the fixed sequence testing procedure. However, subgroup analyses will not only be done for PASI75 and PASI100 but also for PASI90. Additionally, subgroup analyses to assess predictability will also use IGA Response (0/1) (see Section 4.8). Urinalysis will not be analysed in summary tables but will only be included in listings.

Section 14.7 of the protocol describes how multiple imputation should be used to analyse other efficacy endpoints. It is mentioned that the imputation model will use the change from Baseline (instead of actual) values by visit. This statement was omitted from SAP Section 4.2.1.3 as actual values will be used in the imputation algorithm and change from baseline will be calculated based on the imputed values.

### 3.10.1 Changes related to COVID-19

The following changes have been introduced due to the COVID-19 pandemic:

- COVID-19 protocol deviations have been defined in Section 3.4 and the presentation of COVID-19 protocol deviations is described in Section 5.2
- COVID-19 impact on study visits has been assessed and are described in Section 5.1
- COVID-19 Disposition assessments are described in Section 5.1
- Missing data methods for assessing the impact of COVID-19 are described in Section 4.2.1.7
- Data considerations for assessing the impact of COVID-19 on TEAEs including COVID-19 vaccine AEs are described in Section 10.2.1.1 and the associated analysis is described in Section 10.2.2.

## 4 STATISTICAL/ANALYTICAL ISSUES

### 4.1 Adjustments for covariates

The primary efficacy analyses and selected secondary analyses will be adjusted for the following covariates:

- Prior biologic exposure
- Region

### 4.2 Handling of dropouts or missing data

#### 4.2.1 Handling of missing data for efficacy variables

Based on previous studies of biologics in subjects with moderate to severe chronic plaque psoriasis, it is expected that the number of subjects who discontinue prior to Week 16 will be low. For the small percentage of subjects for whom primary endpoint data are unavailable at Week 16, this lack of data is suggestive of an ineffective study treatment, thereby supporting the imputation of nonresponse. Achieving the clinical response and making it through 16 weeks of study treatment are both critical components of the primary outcome. Therefore, non-responder imputation (NRI) is considered an appropriate method for handling missing data.

If a subject discontinues early from the study, all efficacy data that are collected later than 35 days after the last administration of study treatment will be treated as missing and subject to imputation as applicable.

Study variables with multiple components may have rules to account for partial missing data of 1 or more components. Such rules will be defined in section 8 for applicable endpoints. The following rules are outlined for cases where variables are completely missing, including partial missing data where the data handling rules conclude that the variable should be treated as completely missing.

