#### 2.1.3 Other objectives

The other objectives of the study are to demonstrate the effects of bimekizumab on the following aspects of the disease:

- Assess the efficacy of bimekizumab over time
- Assess the change of skin-related quality of life (QOL)
- Assess the change of general health-related QOL
- Assess the change in nail PSO over time in subjects with nail PSO at Baseline
- Assess the change in psoriatic scalp disease over time in subjects with scalp PSO at Baseline
- Assess the change in psoriatic palmoplantar disease over time in subjects with palmoplantar PSO at Baseline
- Assess the change in patient global assessment PSO score
- Assess the change in symptoms of PSO (itch, pain, and scaling) as reported by subjects
- Assess work productivity status
- Assess the safety and tolerability of bimekizumab
- Assess the pharmacokinetics (PK) of bimekizumab
- Assess the immunogenicity of bimekizumab

- Assess the maintenance of efficacy of bimekizumab dosing Q4W versus Q8W
- Assess the safety and efficacy of initiating bimekizumab therapy in subjects who received secukinumab in the double-blind Treatment Period

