During the OLE Period, subjects will attend study visits at Weeks 52, 56, 64, and 72, and then every 12 weeks. At study visits, IMP will be administered in the clinic by sc injection as applicable. In between study visits, subjects will self-inject IMP at home. Subjects who are unable to or decide not to self-inject IMP or those without a family member/friend/caregiver who can help, will not be discontinued, but may continue to visit the site for unscheduled visits for IMP administration only.

All subjects not enrolling in the Open-Label study will have the Week 48 study assessments and will enter the SFU Period.

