### **2.3.3 Study duration per subject**

For each subject not entering the OLE2 treatment period, the study will last a maximum of up to 165 weeks, as follows:

- Screening Period: 2 to 5 weeks
- Double-blind Treatment Period: 48 weeks (final dose at Week 44)
- OLE Period: 96 weeks (final dose at Week 136 for subjects receiving bimekizumab 320mg Q8W and at Week 140 for subjects receiving bimekizumab 320mg Q4W)
- Safety Follow-Up Period: an SFU Visit is planned 20 weeks after the final dose of IMP during the OLE period (this SFU will not apply to subjects directly rolling over from the OLE to the OLE2 Period).

The OLE2 Period will include a 48-week treatment period with a final visit at OLE2 Week 48 and a SFU2 period of 20 weeks after the final dose of IMP administered in the OLE2 Period.

For the subjects in the OLE2 Period, maximum study duration will depend on the time between their participation in the OLE until Week 144 and the start of the OLE2 Period:

- 209 weeks for subjects still being treated in the OLE Period and who will directly roll over to the OLE2 Period at Week 144 visit
- 225 weeks for subjects who have completed Week 144 and the SFU; these subjects will have a 4-week Screening Period before reinitiating treatment in the OLE2 Period. Note: for these subjects, the study duration will not be continuous
- Between 209 and 225 weeks for subjects who have completed Week 144 and are ongoing in the SFU. For these subjects, the maximum study duration will depend upon when they stop the 20-week SFU period to enter the 4-week OLE2 Screening Period.

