## 6.4 Prior and concomitant medications

Medication start and stop dates will be compared to the date of first dose of treatment to allow medications to be classified as either Prior or Concomitant.

Details of imputation methods for missing or partial dates are described in Section 4.2.1.7.

Prior medications include any medications that started prior to the start date of study medication.

Concomitant medications are medications taken at least one day in common with the study medication dosing period (defined as from first dose of study medication [including placebo] up to last dose of study medication + 28 days for the double-blind treatment period, and +28 days or +56 for Q4W and Q8W dosing respectively in the OLE period). Concomitant medications will be summarized separately for the double-blind Treatment Period (SS), the OLE treatment period (OLS).

The number and percentage of subjects taking prior medications (excluding past psoriasis medications) will be summarized by treatment group, overall and by ATC class, presenting Anatomical Main Group (ATC Level 1), Pharmacological Subgroup (ATC level 3), and preferred term. The number and percentage taking concomitant medications will be summarized similarly.

Past psoriasis medications will be captured separately and will also be summarized by treatment group. These medications are not subject to dictionary coding. In addition, subjects who failed past psoriasis biologic treatment will be summarized by reason of failure as captured on the Psoriasis Treatment History CRF module.

The number and percentage of subjects with concomitant vaccines for COVID-19 will be summarized by treatment group, overall and by World Health Organization Drug Dictionary Standardized Drug Grouping (SDG), presenting SDG subgroup, and preferred term. The SDG subgroup Vaccines for COVID-19 will be used to identify vaccines for COVID-19 using the narrow scope; this subgroup is divided further into separate subgroups which is the level that will be presented. The number of individual occurrences of the vaccine for COVID-19 will also be summarized.

By-subject listings of all Prior and Concomitant medications (including COVID-19 concomitant medications), prior and concomitant medications glossary, and psoriasis treatment history will be provided separately for OLE and OLE2 treatment periods. Ongoing concomitant medications from OLE to OLE2 treatment period will be flagged.

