**Table 7-2: Dosing scheme, OLE Period**

Week	48 (1st OLE dose)	Year 2											Year 3													
		52	56	60	64 ab	68	72 ab	76	80	84 ac	88	92	96 ab	100	104	108 ac	112	116	120 ab	124	128	132 ac	136	140		
Bimekizumab 320mg Q4W	●●	●●	●●	●●	●●	●●	●●	●●	●●	●●	●●	●●	●●	●●	●●	●●	●●	●●	●●	●●	●●	●●	●●	●●	●●	●●
Bimekizumab 320mg Q8W	●●		●●		●●		●●		●●		●●		●●		●●		●●		●●		●●		●●		●●	

OLE=Open-Label Extension; Q4W=every 4 weeks; Q8W=every 8 weeks

Notes: A bimekizumab 160mg injection is depicted by a black circle (●).

a The subject's dosing interval will change from Q4W to Q8W at Week 64 or at the next scheduled clinic visit after implementation of Protocol Amendment 5.0 if the subject has already completed the Week 64 visit.

b Subjects whose dosing interval is changed to Q8W should be dosed at this visit and will receive kits for home administration 8 weeks later.

c Subjects whose dosing interval is changed to Q8W should NOT be dosed at this visit and will receive kits for home administration 4 weeks later.

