#### 10.1.4.1 For subjects who do not switch study treatments

Study medication duration (days)

- For subjects who receive Q4W in the Open-Label Extension Period (subjects who discontinue prior to switching to Q8W):
  - Date of last bimekizumab dose in the Open-Label Extension Period – date of first dose in the Open-Label Extension Period + 28 days (for subjects on Q4W dosing)
- For subjects who receive Q8W in the Open-Label Extension Period use the minimum of:
  - Date of last bimekizumab dose in the Open-Label Extension Period – date of first dose in the Open-Label Extension Period + 56 days
  - First dose date in Open-Label Extension 2 Period – date of first dose in the Open-Label Extension Period + 1

Note: If date of last bimekizumab dose in the Open-Label Extension Period + 28 days (or 56 days for subjects on Q8W dosing) extends to a date beyond the final visit date (including PEOT, but not including SFU), then this calculation reverts to:

- Final visit date (including PEOT, but not including SFU) – date of first dose in the Open-Label Extension Period + 1.

Note: For subjects who die, if date of last bimekizumab dose in the Open-Label Extension Period + 28 days (or 56 days for subjects on Q8W dosing) extends to a date beyond the date of death, then this calculation reverts to:

- Date of death – date of first dose in the Open-Label Extension Period + 1.

Time at risk (days)

- For all subjects, use the minimum of the following:
  - Date of last dose in the Open-Label Extension Period – date of first dose in the Open-Label Extension Period + 140 days,
  - Date of first dose in OLE2 - date of first dose in the Open-Label Extension Period + 1 day
  - Date of last clinical contact in OLE and SFU – date of first dose in the Open-Label Extension Period + 1.
  - Date of death – date of OLE first dose

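### In the OLE Period the single 35-day efficacy cut-off for early leavers is shorter than the 56-day Q8W dosing interval, so some on-interval Q8W assessments are discarded

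*SAP*

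**What the plan says.** Section 4.2.1 sets the rule for anyone who leaves the study early: "all efficacy data that are collected later than 35 days after the last administration of study treatment will be treated as missing", and the data are then imputed where applicable. Section 4.2.1.7 repeats the 35 days. Neither place distinguishes regimen or period, and neither says where the figure comes from.

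The OLE schedule is given in three places:
- The legend to Table 7-2 reads "OLE=Open-Label Extension; Q4W=every 4 weeks; Q8W=every 8 weeks", and the table shows no placebo injections.
- Section 2.3.3 gives the last doses: "final dose at Week 136 for subjects receiving bimekizumab 320mg Q8W and at Week 140 for subjects receiving bimekizumab 320mg Q4W".
- Section 2.3.2.4 gives the clinic visits: "subjects will attend study visits at Weeks 52, 56, 64, and 72, and then every 12 weeks".

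Two other rules do depend on regimen. For concomitant medication, Section 6.4 extends the dosing period by "28 days or +56 for Q4W and Q8W dosing respectively in the OLE period". For exposure on Q8W, Section 10.1.4.1 uses "Date of last bimekizumab dose in the Open-Label Extension Period – date of first dose in the Open-Label Extension Period + 56 days", and its truncation note refers to "28 days (or 56 days for subjects on Q8W dosing) extends to a date beyond the final visit date".

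Section 3.3 maps a withdrawal (PEOT) visit to the scheduled visit it coincides with, or otherwise to the next one, and counts it as observed there. Section 4.2.1.3 applies NRI to other binary variables and MI to continuous ones. Section 2.1.3 lists among the other objectives: "Assess the maintenance of efficacy of bimekizumab dosing Q4W versus Q8W".

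**The concern.** A cut-off of this kind should remove assessments made after drug cover has lapsed. In the double-blind period 35 days is long enough for every arm, because the Q8W arm receives placebo at the intermediate visits and so has an injection every 4 weeks. In the OLE that no longer holds. A Q8W subject can be assessed exactly when the next dose falls due and still be past the limit.

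The SAP treats that time point differently elsewhere. Exposure and concomitant medication rules run to 56 days for OLE Q8W. A Q8W completer's Week 144 assessment, 56 days after the Week 136 dose, is kept. Only the early leaver's assessment at the same distance from dosing is removed.

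What is at stake is an observed response reported as a non-response, more often on one regimen than on the other. The OLE summaries include sequences in which Week 48 PASI90 responders were randomized 1:1 to Q4W or Q8W (Sections 2.3.2.4 and 3.6), and that is where a reader would look for maintenance of response by regimen.

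**Working it through.** **Inputs.** Cut-off 35 days (Section 4.2.1). OLE doses: Q4W at Weeks 48 to 140 every 4 weeks, Q8W at Weeks 48 to 136 every 8 weeks (Table 7-2, Section 2.3.3). OLE visits: Weeks 52, 56, 64, 72, then every 12 weeks to 144 (Section 2.3.2.4). Visit windows: ±7 days from Week 28 to Week 72, ±14 days from Week 76 to Week 144 (Section 3.1).

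**The 35 days.** The SAP gives no derivation to reproduce. The figure equals 28 + 7, one Q4W interval plus a 7-day window; that reading is an inference.

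**Part of the interval lost.** For Q8W, 56 − 35 = 21 days (days 36 to 56), and 21/56 = 37.5%. For Q4W, 28 < 35, so nothing is lost within the interval.

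**Days since the last scheduled dose before each visit**, 7 × (visit week − last dose week):

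| Visit week | 52 | 56 | 64 | 72 | 84 | 96 | 108 | 120 | 132 | 144 |
|---|---|---|---|---|---|---|---|---|---|---|
| Q8W | 28 | 56 | 56 | 56 | 28 | 56 | 28 | 56 | 28 | 56 |
| Q4W | 28 | 28 | 28 | 28 | 28 | 28 | 28 | 28 | 28 | 28 |

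The Q4W row assumes Q4W dosing continues; under Protocol Amendment 5.0 those subjects move to Q8W from Week 64. Week 144 is the completion visit and the rule applies only to early leavers, so it is left out. That leaves 5 of 9 visits past 35 days on Q8W (Weeks 56, 64, 72, 96, 120) and 0 of 9 on Q4W.

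**Example before any switch.** A subject leaves at Week 56 without being dosed there. On Q8W the last dose was Week 48: 7 × (56 − 48) = 56 days, so the assessment is discarded. On Q4W the last dose was Week 52: 7 × (56 − 52) = 28 days, so it is kept.

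**Size under NRI at one affected visit.** Fall in response rate = (proportion leaving in the visit interval) × (proportion of leavers still responding) × (proportion of leavers seen after day 35). All three inputs are assumptions:
- Low: 0.01 × 0.50 × 0.375 = 0.0019, about 0.2 percentage points.
- Middle: 0.02 × 0.90 × 1 = 0.018, or 1.8 points.
- High: 0.05 × 0.90 × 1 = 0.045, or 4.5 points.

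**Interval plus window.** To Week 72: Q4W 28 + 7 = 35 days, Q8W 56 + 7 = 63 days. From Week 76: Q4W 28 + 14 = 42 days, Q8W 56 + 14 = 70 days. With these limits none of the nominal OLE visits falls past the cut-off on either regimen.

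**The case against.** The strongest reply is that little depends on this. OLE results are descriptive, each affected leaver loses about one mapped visit, and the blinded re-randomized Q4W/Q8W comparison is in the Maintenance Period, where injections are 4-weekly. That stands, and it limits the weight of the point.

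Further replies also stand in part:
- Five of the nine visits is a count of nominal visits, not of withdrawals. Weeks 56, 64, 72, 96 and 120 are also Q8W dosing visits, and a subject assessed and dosed there who withdraws later keeps that assessment.
- With the ±14-day window, a Q4W assessment can itself fall as late as day 42. The contrast between regimens is exact only at nominal timing.
- Section 10.1.2 already uses 56 days for Q8W exposure in the Maintenance Period, where 35 days is adequate for efficacy. The exposure rule alone therefore does not prove an error. The stronger arguments are the absence of placebo in the OLE and the retention of completers at day 56.
- Section 4.2.1.1 makes discontinuation of IMP itself a reason for non-response. That wording is confined to the Week 16 primary variable. The general NRI definition in Section 4.2.1.5 rests on missing data, so in the OLE it is the cut-off that creates the non-response.

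A reader might infer more than the SAP supports:
- **That the tested hypotheses are biased.** H1 to H6 and the Week 16 and Week 48 analyses are unaffected if placebo counts as study treatment. Section 3.2 says so for the first dose, but Section 4.2.1 does not say it for the last.
- **That OLE2 is affected in the same way.** OLE2 efficacy uses observed cases (Section 4.2.1.6), which already exclude subjects off treatment (Section 4.2.1.5).
- **That the contrast between regimens lasts to Week 144.** Q4W subjects move to Q8W under Protocol Amendment 5.0, while groups stay labelled by the Week 48 regimen. The difference is clearest before the switch; afterwards former Q4W subjects meet the same cut-off.
- **That every endpoint is pushed downward.** That direction holds for NRI binary endpoints. Continuous ones are imputed from the subject's other visits, with no evident direction, and ordinal ones use observed cases.

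**Conclusion.** The point holds for the OLE Period. A 35-day limit does not fit a 56-day dosing interval without placebo, and it disagrees with the regimen-specific rules in Sections 6.4 and 10.1.4. The consequence is loss of Q8W leavers' assessments on days 36 to 56, with observed binary responses turned into non-responses at one mapped visit each.

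The size cannot be derived from the SAP. The range of about 0.2 to 4.5 percentage points at an affected visit rests wholly on the assumed leaving, response and timing proportions, and its upper end needs all three at their maximum. The confirmatory conclusions are not in question, provided placebo injections count. The point deserves correction because it distorts a descriptive comparison that serves a stated objective and the remedy is cheap.

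**What to change.** In Section 4.2.1, define the efficacy cut-off by the regimen at the last dose, as the dosing interval plus the applicable visit window:
- Double-blind period: keep 35 days, and state that placebo injections count as study treatment.
- OLE Q4W: 28 days plus 7 (to Week 72) or plus 14 (from Week 76), that is 35 or 42 days.
- OLE Q8W: 56 days plus 7 or plus 14, that is 63 or 70 days.

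OLE2 needs no separate rule. If 35 days is meant to stand for OLE Q8W, the SAP should give the reason and report how many observed assessments the limit removes, by regimen and visit.

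The cost is a sentence or two in the SAP, one programming condition keyed to the regimen at last dose, and a rerun of any OLE efficacy outputs already produced. No dosing or data collection changes.

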#### **4.2.1.1 Handling missing data for the primary efficacy variable**

The analysis of the primary efficacy variable will use NRI for handling of missing data. That is, subjects with missing data or who have discontinued IMP prior to Week 16 will be considered as non-responders for the primary analysis.

In addition, sensitivity analyses using multiple imputation (Markov-Chain Monte Carlo method) (MI-MCMC)/monotone regression, last observation carried forward (LOCF) and observed case (OC) method will be performed which will assess the impact of different methods of handling missing data. These methods are described in Section 8.1.3.1 to Section 8.1.3.4.

#### **4.2.1.2 Handling missing data for the secondary efficacy variables**

Missing data for the secondary efficacy variables (which are all binary) will be imputed using NRI. Additionally, MI-MCMC/monotone regression and OC methods will be performed as sensitivity analysis. If the imputation model cannot converge, LOCF will be used. The same analyses are detailed in the analysis for the primary efficacy variable in Section 8.1.3.1 and Section 8.1.3.2.

Additional methods for handling missing data to assess the impact of the COVID-19 global pandemic on planned statistical analyses are detailed in Section 4.2.1.7.

#### **4.2.1.3 Handling missing data for the other efficacy variables**

For other binary efficacy variables, missing data will be imputed using NRI as primary method.

For other continuous efficacy variables, multiple imputation (MI) will be used to impute missing data when possible. If the imputation model cannot converge, last observation carried forward (LOCF) will be used. The MI procedure will be similar to sensitivity analysis #1 described in Section 8.1.3.1 with the following differences:

1. No dichotomization will be necessary.
2. Instead of using the stratified Cochran-Mantel-Haenszel (CMH) test, the imputed data sets will be combined, and simple means and standard errors will be calculated using Rubin's rules (via SAS PROC MIANALYZE). For calculation of other descriptive statistics such as the median, minimum and maximum, Rubin's rules do not apply. Multiple imputation estimates will be computed by simply averaging the estimates from the multiple repetitions of the imputation algorithm.

For other ordinal variables (IGA score, EQ-5D-3L and Patient Global Assessment of PSO), OC method will be applied as the primary analysis method. No imputation is applied.

